PER ^b -3			4mg	4mg	4mg	4mg	4mg	4mg
Partial NP ^c			X	X		X	X	
Full NP ^d	X	X			X			X
TEAEs ^e	X	X	X	X	X	X	X	X

Testing is at the end of each week.

^aBL = baseline visit.

^bPER = perampanel.

^cPartial NP = partial neuropsychological battery on non-clinic visit weeks refers to online CNS-Vital Signs computerized cognitive tests and behavioral questionnaires (POMS-total, AEP, & QOLIE-89 cognitive scores, which will be mailed back).

^dFull NP = full neuropsychological battery includes Non-computerized cognitive tests and the Partial NP (questionnaires and online CNS-Vital Signs computer tests).

^eTEAEs = treatment emergent adverse events.

The investigative team will monitor each subject's progress and safety during ASM treatment periods. Subjects will remain in their treatment arm for a total of 6 weeks.

D. Enrollment Goals

Previous studies indicate that an enrollment of 103 subjects will be required to obtain 76 evaluable subjects. See Statistical Section for power analysis.

E. Visit-Specific Treatment and Evaluation Sequence

Subjects will be randomly assigned to one of four possible titration schedules. Each titration schedule lasts 6 weeks.

At all visits, subjects will be advised on drug compliance and avoidance of medications which may adversely effect the results of cognitive function testing. Adverse events will be documented on the appropriate case report form. Appointments will be made for follow up visits and care will be taken to schedule all cognitive and behavioral function testing for a given subject at the same time of the day. Dosing of the study medication should be at approximately the same time of day (e.g., before the participant goes to sleep). However, due to the long half-life of perampanel, this is not critical. The time of testing and time of last 2 doses will be recorded.

The timetable for the study is listed in Appendix A. This is a visit-by-visit description of the events scheduled for each visit.

Visit 1 Screening Visit (-1 weeks prior to randomization)

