Subjects will be screened to assure they meet all of the inclusion criteria and none of the exclusion criteria. All eligible subjects will be required to give informed consent. A complete history, full physical examination, full neurologic examination, vital signs, laboratory screening (including urine pregnancy test for women of childbearing potential), urine drug screen, IQ screen with Peabody Picture Vocabulary Test, full cognitive battery (see below), and lifetime assessment of suicidal ideation/behavior measured by the Columbia-Suicide Severity Rating Scale (C-SSRS) will be obtained.

Visit 2 Baseline/Randomization (Study week 0)

At this visit all subjects who had successfully completed all screening tests and had no significant abnormalities on baseline laboratory, physical exam, neurologic exam, or IQ testing will be randomized to study drug. At this visit, neuropsychological testing will be conducted before the first dose of study drug is administered. Subjects will be randomized and study drug will be dispensed.

Visit 3 Home testing (Study week 1)

At this visit, a partial neuropsychological assessment of cognitive function and behavioral testing will be performed. The assessments at this visit consist of online CNS-Vital Signs computerized cognitive tests and behavioral questionnaires (Profiles of Mood States

(POMS), Adverse Events Profile (AEP), & cognitive/behavioral subsets of QOLIE-89). Partial neuropsychological assessment will be conducted. Telephone contact will be made to check on adverse events and to encourage compliance.

Visit 4 Home testing (Study week 2)

At this visit, a partial neuropsychological assessment of cognitive function and behavioral testing will be performed. The assessments at this visit consist of online CNS-Vital Signs computerized cognitive tests and behavioral questionnaires (Profiles of Mood States (POMS), AEP, & cognitive/behavioral subsets of QOLIE-89). Partial neuropsychological assessment will be conducted. Telephone contact will be made to check on adverse events and to encourage compliance.

Visit 5 Clinic testing (Study week 3)

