Fifteen words are presented sequentially for 2 seconds each on the computer screen and subjects are instructed to remember the words. Following their presentation, the 15 target words are presented in addition to new words, and the subject indicates if the word is new (not presented) or old (a member of the original presentation list). The duration of instructions and testing is approximately 3 minutes.

Results are reported as follows:

- Correct hits (immediate)
- Correct passes (immediate)
- Total Correct hits + passes (immediate) – This is a primary measure for Z score.

1c. Visual memory immediate assessment:

Fifteen shapes are presented sequentially for 2 seconds each on the computer screen, and subjects are instructed to remember the shapes. Following their presentation, the 15 target shapes are presented in addition to new shapes, and the subject indicates if the shape is new

(not presented) or old (a member of the original presentation list). The duration of instructions and testing is approximately 3 minutes.

Results are reported as follows:

- Correct hits (immediate)
- Correct passes (immediate)
- Total Correct hits + passes (immediate) – This is a primary measure for Z score.

1d. Symbol digit coding:

As a measure of processing efficiency, symbols are presented on the computer screen and the subject types in numbers that correspond to each symbol based upon a response key. The duration of instructions and testing is approximately 4 minutes.

Results are reported as follows:

- Correct responses – This is a primary measure for Z score.
- Errors
- Correct responses – Errors – This is a primary measure for Z score.

1e. Shifting attention test:

As a measure of set shifting attention and executive function, the subject assesses a series of targets and rules and responds by pressing the appropriate shift key. The duration of instructions and testing is approximately 3 minutes.

Results are reported as follows:

- Correct responses
- Errors
- Correct responses – Errors – This is a primary measure for Z score.

1f. Dual task test:

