- Total Correct responses– This is a primary measure for Z score.

1i. Visual memory delayed assessment:

This is a measure of delayed memory in which the 15 target shapes from the original list are presented interspersed with 15 foils. The subject indicates if the shape is new (not previously presented) or old (a member of the original presentation list). The duration of instructions and testing is approximately 1 minute.

Results are reported as follows:

- Correct hits (delayed)
- Correct passes (delayed)
- Total Correct responses— This is a primary measure for Z score.

2. Components for non-computerized cognitive and behavioral assessments:

The non-computerized cognitive and behavioral battery performance measures consist of MCG paragraph memory, symbol digit modalities test, Stroop test, and POMS. A detailed description of each of these follows.

2a. Peabody picture vocabulary test:

At Screening, the PPVT (third edition) will be used to assess IQ at enrollment. The PPVT is an individually-administered test of receptive vocabulary (of standard English) for children and adults from 2.5 through 90 years old. This test requires examinees to examine a series of 4 pictures and choose which best represents the meaning of a stimulus word that is presented orally by the examiner (Dunn and Dunn, 1997).

This is screening measure and is not used in analyses.

2b. MCG paragraph memory:

The MCG paragraph memory test includes a matched set of short stories that were previously developed and have been shown to be sensitive to the side effects of anticonvulsants ([name] et al, 1993). On each test day, the subjects will be read 1 of the short stories. Free immediate and delayed (approximately 15-minute) recall will be obtained.

The primary measure for Z score is the % correct for delayed recall.

2c. Symbol digit modalities test:

The SDMT is a measure of cognitive processing involving coding which is sensitive to drug effects. This is a complex graphomotor transcription task that requires the subject to transcribe symbols to numbers as quickly as possible employing a combination of direct visual identification and/or short-term memorization. Symbols with empty squares are presented, and the subject's task is to fill in the corresponding number as quickly as possible during a 90-second interval (Smith, 1973). Results are scored based on number correct in 90 seconds, which is the primary measure for Z score.

2d. Stroop test:

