 - d. Consent is withdrawn. Subjects will be encouraged to complete the study, although they may withdraw at any time without prejudice.
4. Subject replacement.

Subjects who are dropped from the study prior to completion of all cognitive testing will not be replaced.

Subjects who are withdrawn prior to completion of at least one set of cognitive testing on treatment drug (i.e., prior to visit 5/study week 3) may be replaced.

5. Follow-up of discontinued patients

Subjects who receive study drug and are discontinued from the study will have all safety assessments completed, including a complete physical examination and laboratory evaluation including chemistry, hematology with differential, urinalysis and urine pregnancy test as required at study termination. This testing should be done as soon as possible. Medical follow-up of any severe adverse events or clinically significant abnormal laboratory values will continue until the abnormality resolves, and adequate medical explanation is apparent. Such data will be provided to Eisai.

X. STATISTICAL EVALUATION

A. Sample Size

We assume that the 4 groups (3 PER treatments and a placebo group) are equally spaced (in terms of z-score) at the time point of maximum drug effects (end week 1 for 4mg group and end week 3 for titration to 2mg x2wks then 4mg group), with a maximum difference of 0.24 (which is the difference between the placebo group and treatment at max effect). We then assume that over the 4 visits after max drug effect the z-scores get closer together until

they are equal at the treatment week 6th. The calculation indicates that at least 18 subjects are needed in each group to have 80% power. Since there are 4 groups, the total sample at least finishing assessment at end of week 6 (event 8) would be $19 \times 4 = 76$. Enrollment will include 20% (n=15) more to account for dropouts prior to assessment at end of visit 2 (baseline), and ~15% (n=12) more for dropouts before end of event 8 (treatment week 6). Thus, the total enrollment sample will be 103 subjects.

In summary, the 4 total groups (3 PER treatment, 1 placebo) would need at least 19 subjects per group (76 total), and total enrollment would be rounded to 105 to account for dropouts.

B. Methodology for statistical analysis

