The parameters of interest are listed in Section VII. Descriptive statistics will be used to provide an overview of the primary, secondary, and other variable results. For categorical parameters, the number and percentage of subjects in each category will be presented. The denominator for percentages will be based on the number of subjects appropriate for the purpose of analysis. For continuous parameters, descriptive statistics will include number of subjects, mean, standard deviation (SD), median, minimum, and maximum. Unless otherwise specified, baseline neuropsychological data will be based on the Visit 2 assessments.

Study question 1: What are the behavioral, cognitive or other side effects of perampanel at different titration rates in healthy volunteers?

The primary outcome variable will be the overall neuropsychological composite z-scores for the objective and subjective measures combined.

Study question 2: What is the time course of habituation to objective vs. subjective neuropsychological (e.g., cognitive and behavioral) side effects of perampanel?

The primary outcome variable will be the neuropsychological composite z-scores for the objective and subjective measures, which will be analyzed separately.

The objective measure z-score will be calculated by averaging overall computerized and noncomputerized cognitive z scores, which are calculated by averaging individual z-scores of selected performance measures from the computerized cognitive test battery (i.e., average of z-scores for the domain scores for executive function and for processing speed) and from the noncomputerized cognitive test battery (i.e., average of individual z-scores for MCG immediate, MCG delayed, SDMT, and Stroop-average score). The subjective measure z-score will be calculated by averaging the individual z-scores for AEP, POMS, and QOLIE-cognitive questions (average of 3 scores from QOLIE). These z-scores will be assessed by a 4 (titration rate) \times 6 (time: weeks 1-6) ANCOVA controlling for scores at Baseline (visit 2) using an intent-to-treat analysis for those receiving neuropsychological testing at least at the end of week one. Imputations will be employed for dropout after week one.

We will control for differences across groups in age, gender, and personal/family history of psychiatric disorders.

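### The objective and combined composites cannot be computed as defined at weeks 1, 2, 4 and 5, and no rule says how to score those weeks in the primary 4 x 6 ANCOVA

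*Combined protocol and SAP*

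**What the plan says.** Section X.B averages two parts into the objective z-score. The computerized part is the CNS Vital Signs executive function and processing speed domains. The other part comes "from the noncomputerized cognitive test battery (i.e., average of individual z-scores for MCG immediate, MCG delayed, SDMT, and Stroop-average score". The subjective z-score averages AEP, POMS and the QOLIE cognitive items. Question 1 uses the objective and subjective measures combined; question 2 uses each separately. All enter a model with four titration groups by "6 (time: weeks 1-6) ANCOVA controlling for scores at Baseline (visit 2").

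The schedule is different. Under VI.C, footnote c, the "partial neuropsychological battery on non-clinic visit weeks refers to online CNS-Vital Signs computerized cognitive tests and behavioral questionnaires". VI.E repeats this for the home visits at weeks 1, 2, 4 and 5: "The assessments at this visit consist of online CNS-Vital Signs computerized cognitive tests and behavioral questionnaires". Appendix A agrees. MCG, SDMT and Stroop belong to the full battery, which is given at screening, baseline, week 3 and week 6.

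X.A puts the maximum drug effect at "end week 1 for 4mg group and end week 3 for titration to 2mg x2wks then 4mg group", with the groups converging until "they are equal at the treatment week 6th".

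**The concern.** Two of the three primary composites contain tests that are not given at four of the six analysed weeks. The analyst must therefore invent a rule for those weeks, and must also choose which Visit 2 score serves as the covariate.

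The choice affects what the trial can show. The objective is to compare titration rates, and question 2 asks how effects fade. X.A places the 4 mg arm's peak in a computerized-only week and the two-week titration arm's peak in a full-battery week. Depending on the rule adopted, the first peak is either dropped or measured on a different score from the second. X.B relies on a single composite to avoid multiple comparisons, and that argument is weaker if its scoring stays open until data are in hand.

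**Working it through.** **1. Definition against schedule (no assumptions)**

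| Week | CNS Vital Signs | MCG, SDMT, Stroop | Questionnaires | Objective and combined score as defined |
|---|---|---|---|---|
| Baseline | yes | yes | yes | computable |
| 1, 2 | yes | no | yes | not computable |
| 3 | yes | yes | yes | computable |
| 4, 5 | yes | no | yes | not computable |
| 6 | yes | yes | yes | computable |

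The scores exist in 2 of 6 weeks, or 2 x 4 = 8 of 24 group-by-week cells. With 76 completers that is 76 x 2 = 152 of 76 x 6 = 456 subject-visits; 304 (67%) lack the paper half by design. The subjective score exists in all six weeks.

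**2. Is there a rule?**

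- X.B imputes for subjects who leave after the first week. These subjects have not left.
- X.D rules out imputation and asks that all data be used as fully as possible. That sentence closes a paragraph on who is evaluable; it does not say how to score a composite.
- The replacement rule in the discontinuation section places the first on-treatment set of cognitive testing at visit 5 (week 3), which fits a complete-score reading.
- X.B reserves the full battery by name for secondary outcome 1, which fits a partial-battery reading of the weekly analysis. X.B's own definition of the weekly score contradicts that reading.

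The text does not settle the choice.

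**3. The plan's own figures**

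19 x 4 = 76 and 76 + 15 + 12 = 103 reproduce. The 18 per group cannot be reproduced, because no SD, correlation or primary alpha is given. As one example, a two-arm comparison of 0.24 at two-sided 0.05 and 80% power with 18 per group implies SD = 0.24 / (2.802 x √(2/18)) = 0.257. The mismatch in step 1 does not depend on this.

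**4. Size if available components are averaged (illustrative)**

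Let E be the effect on the computerized tests and kE the effect on the paper tests. Home weeks show E; weeks 3 and 6 show E(1 + k)/2. The distortion is E(1 − k)/2.

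- For E = 0.24: 0.12 at k = 0, 0.06 at k = 0.5, 0 at k = 1, and 0.06 in the other direction at k = 1.5.
- Assume the 4 mg arm fades linearly from −0.24 at week 1 to 0 at week 6 (X.A states no shape): −0.24, −0.192, −0.144, −0.096, −0.048, 0. At k = 0, week 3 reads −0.144/2 = −0.072. Recovery from week 2 to 3 then looks like 0.120 instead of 0.048, followed by a false worsening of 0.024 at week 4.
- Peak gap under X.A's equal spacing, taking the 4 mg arm as largest (−0.24) and the two-week titration arm as smallest (−0.08), an assignment X.A does not state: the true gap of 0.16 reads 0.20, 0.18, 0.16 or 0.14 at k = 0, 0.5, 1 or 1.5. The distortion is at most 0.04.

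**5. False-significance rates for two contrasts the plan does not name**

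Assumed: 19 per arm, SD σ for each battery, time correlation 0.6, battery correlation 0.5, k = 0, noncentral t with 36 df. The two-battery average has variance σ²(1 + 0.5)/2 = 0.75σ². Its covariance with the computerized score at another week is 0.6 x 0.75σ² = 0.45σ².

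- Change from week 5 to 6, constant effect of 0.24 (not X.A's assumption): variance σ²(1 + 0.75 − 0.90) = 0.85σ²; SE = σ√(2 x 0.85/19) = 0.299σ.
- 4 mg arm at week 1 against two-week titration arm at week 3, each minus placebo, with true peaks equal at −0.24 (a departure from X.A's spacing). Adjusted for the two-battery baseline, the residual variances are 0.73σ² and 0.48σ², with covariance 0.18σ² within placebo. SE = σ√((2 x (0.73 + 0.48) − 2 x 0.18)/19) = σ√(2.06/19) = 0.329σ.

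| SD | 0.25 | 0.40 | 0.60 | 0.71 | 0.80 |
|---|---|---|---|---|---|
| Week 5 to 6, false 0.12 z | 35% | 16% | 10% | 8.5% | 8% |
| Peak contrast, false 0.12 z | 29% | 14% | 9% | 8% | 7% |

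At k = 0.5 the false difference is 0.06 z, and both rates are 11 to 12% at SD 0.25 and about 6% at SD 0.71 to 0.80.

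**The case against.** The strongest reply is that the intent is clear enough: the weekly analysis would use whatever is given weekly, and the full battery is kept for secondary outcome 1. If the partial battery were used at every week, content would not change and there would be no distortion. That is a reasonable design, but it is not what X.B defines, so it has to be written down.

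Three further replies limit the harm, and they stand.

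- **Content change is not bias by itself.** It needs unequal drug effects on the two batteries. The case of no paper effect sits badly with the protocol, which says the MCG stories "have been shown to be sensitive to the side effects of anticonvulsants" and describes SDMT in similar terms. Once the drug effect is zero, as X.A assumes at week 6, there is nothing to distort.
- **The high error rates need a small SD.** If component z-scores have unit variance (an assumption), the mean of two non-negatively correlated domains has SD of at least √0.5 = 0.71, where the rates are 8 to 8.5%. Against this, step 3 shows that X.A may itself imply a small SD, so the range stays open.
- **The planned test barely moves.** In a simulation of the overall group-by-time test under the linear fade at SD 0.25, power was 83% with constant content and 80% with mixed content and no paper effect.

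A reader might infer that available-component averaging is the plan's default, that the habituation result will be biased, or that the primary test carries about 30% false positives. The documents support none of these. The default is unstated, the bias is conditional, and the 29 to 35% rates belong to unplanned contrasts at one assumed SD.

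**Conclusion.** The mismatch is established from the text alone. The objective composite (half of question 2) and the combined composite (question 1) have no executable definition at weeks 1, 2, 4 and 5. This is a stated rule that fails on the plan's own schedule, and it should be fixed before analysis. It does not make the whole primary analysis impossible: the subjective composite runs as written, and a consistent weekly objective score can be built from data already collected.

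The consequence depends on the rule chosen. Complete scores lose four of six weeks, including the assumed 4 mg peak. Available components risk a distorted habituation curve and distorted peak comparisons, but only with unequal battery effects. The distortion is 0.12 z of 0.24 with unaffected paper tests, and at most 0.04 z in the peak gap under X.A's equal spacing for paper effects from none to 1.5 times the computerized effect. False significance in contrasts the plan does not name is about 7 to 8.5% at SD 0.7 to 0.8, and reaches about 30 to 35% only at SD 0.25. These sizes rest on assumed SDs, correlations, fade shape and arm ordering.

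**What to change.** In X.B, for the 4 x 6 primary analysis:

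1. Build the weekly objective score only from components collected at baseline and at every one of weeks 1 to 6, namely CNS Vital Signs executive function and processing speed.
2. Build the combined score from that and the subjective score (AEP, POMS, QOLIE) with prespecified weights, for example equal objective and subjective halves. X.B gives no separate formula for it now.
3. Use the identically built Visit 2 score as covariate.
4. Keep secondary outcome 1 as it is, and add a full-battery objective composite at weeks 3 and 6 as a secondary analysis.
5. State in X.A that the 0.24 difference and the 18 to 19 per group are assumed to apply to the redefined score, or justify them again.

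No new visits or data are needed, but this is more than a wording change. It redefines the primary outcome for question 1 and the objective half of question 2. MCG, SDMT and Stroop would be tested only at weeks 3 and 6, although the protocol calls MCG and SDMT drug-sensitive, and memory would leave the weekly score. If the sponsor wants memory there, the CNS Vital Signs verbal and visual memory tests belong to the computerized battery, and VII.B already says of each total score: "This is a primary measure for Z score". X.B does not list them, so they would have to be added explicitly. Analysing the computerized and paper scores separately is a less invasive alternative; it too must be prespecified.

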This method with a similar overall score has been employed in prior investigations. This approach avoids potential Type I errors from multiple statistical comparisons and Type II errors resulting from reduced statistical sensitivity as a result of correcting for multiple comparisons. Analyses of individual components of the computer and neuropsychological assessment are secondary endpoints meant to evaluate sensitivity of the primary endpoint and examine the pattern of neuropsychological effects. All other endpoints are supportive and are safety assessments. Hence no adjustments for multiplicity are planned. P-values for these safety variables are not meant to show superiority and thus testing each of these variables at the $p=0.05$ level without multiplicity adjustment is a more conservative approach, which is appropriate for safety assessments and for secondary analyses of the pattern of impairments. The importance of the results should be evaluated in terms of actual differences and the risk/benefits offered by the drug to the patients.

The secondary outcome variables will be:

1. Compare titration rates for changes from Baseline (visit 2) to the end of titration (study week 3) and end of maintenance (study week 6) using Z-scores from full neuropsychological battery. The outcome variable for this analysis will be an overall neuropsychological composite Z-score, calculated by averaging individual z-scores of the selected performance measures from the computerized cognitive test battery (i.e., z-scores for the domain scores for executive function and processing speed), the average for individual Z-scores for AEP, POMS, QOLIE-cognitive questions (average of 3 scores), and the noncomputerized cognitive scores (i.e., average of z-scores for MCG immediate, MCG delayed, SDMT, Stroop-average score).
2. Compare titration rates for TEAEs and dropouts due to TEAEs across visits 3-8 (i.e., weeks 1-6).
3. Separate comparisons of titration rates for behavioral overall scores and cognitive overall scores.
4. Comparisons of titration rates and habituation over time for individual measures.

Summary statistics will be calculated by treatment for each evaluation of antiepileptic blood levels (ABLs). Additional analyses of data will be performed which take the ABLs into account. Linear correlations of plasma concentrations and the overall composite and individual score variables will be plotted with a fitted regression line superimposed for each condition.

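### Secondary outcome 1 compares changes from Visit 2 with no baseline covariate, and secondary outcome 4 states no baseline handling, although the primary composites are adjusted for the Visit 2 score (minor)

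*Combined protocol and SAP*

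**What the plan says.** All of this is in section X.B of the combined protocol and SAP, except the arm size, which is in X.A.

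- **Primary composites.** The z-scores for both study questions go into a titration-rate by week model described as "ANCOVA controlling for scores at Baseline (visit 2) using an intent-to-treat analysis".
- **Secondary outcome 1.** "Compare titration rates for changes from Baseline (visit 2) to the end of titration (study week 3) and end of maintenance (study week 6". The next sentence defines the variable: "The outcome variable for this analysis will be an overall neuropsychological composite Z-score". No model, test or covariate is named.
- **Secondary outcome 4.** "Comparisons of titration rates and habituation over time for individual measures". Nothing is said about baseline.
- **Other covariates.** "We will control for differences across groups in age, gender, and personal/family history of psychiatric disorders". This sentence is not tied to a particular analysis, and the Visit 2 score is not in its list.
- **Arm size.** X.A says that the four groups "would need at least 19 subjects per group (76 total".

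**The concern.** Within one section, the primary analysis is given an explicit baseline-adjusted model and the first secondary outcome is given a comparison of changes. The general covariate sentence does not close the gap. An analyst following the text would most naturally subtract the Visit 2 score and compare the differences between arms.

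Subtraction fixes the slope on baseline at 1. ANCOVA estimates it, and with equal variances at the two visits the slope equals r, which is below 1 for any test with imperfect retest reliability. The change score therefore over-corrects: an arm that starts high by chance will appear to decline relative to the others.

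What is at stake is precision in small arms, and consistency. X.B uses the component analyses to check the sensitivity of the primary endpoint and to describe the pattern of effects. If they use a different estimator, a disagreement with the primary result may come from the method and not from the drug.

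**Working it through.** **The plan's own figure.** X.A states that "at least 18 subjects are needed in each group to have 80% power". This can be neither reproduced nor refuted, because the SD, the within-subject correlation, the sidedness and the test are not given. Nothing below depends on it. The arm size used is the 19 per group that X.A adopts (19 × 4 = 76).

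**Inputs**

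- n = 19 per arm, from X.A.
- r, the correlation between the Visit 2 score and the week-3 or week-6 score: not in the documents. Assumed range 0.5 to 0.9.
- SD of the composite: not in the documents. Results are in units of that SD.
- Equal variances at baseline and follow-up, and a common slope across arms: assumed.

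**Formulas (per subject, SD = 1)**

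- Change score: Var = 2(1 − r)
- ANCOVA: Var = 1 − r²
- Ratio: (1 − r²) / [2(1 − r)] = (1 + r)/2
- Subjects per arm for a change score to match ANCOVA at 19: 19 / [(1 + r)/2]

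| r (assumed) | Var, change | Var, ANCOVA | Ratio | n per arm to match 19 |
|---|---|---|---|---|
| 0.5 | 1.00 | 0.75 | 0.75 | 25.3 |
| 0.7 | 0.60 | 0.51 | 0.85 | 22.4 |
| 0.8 | 0.40 | 0.36 | 0.90 | 21.1 |
| 0.9 | 0.20 | 0.19 | 0.95 | 20.0 |

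In terms of power, if a change-score comparison had 80% power, ANCOVA on the same data would have about 90%, 86%, 84% and 82% respectively.

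**Where the extra variance comes from.** Algebraically, 2(1 − r) = (1 − r²) + (1 − r)². The second term is the variance from the part of the baseline difference that the change score leaves in the contrast. The standard error of the baseline difference between two arms of 19 is √(2/19) = 0.324 SD. A difference of that size shifts the change contrast, in the opposite direction, by (1 − r) × 0.324:

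- r = 0.5: 0.162 SD
- r = 0.7: 0.097 SD
- r = 0.8: 0.065 SD
- r = 0.9: 0.032 SD

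The lost precision and the retained imbalance are therefore one cost seen from two sides.

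**Price of estimating the slope.** Four arms of 19 leave 76 − 4 = 72 within-arm degrees of freedom. The expected variance inflation is about 1 + 1/(72 − 2) = 1.014, or 1.4%. It turns the ratios into about 0.76, 0.86, 0.91 and 0.96.

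**Simulation check** (four arms of 19, 8000 trials per value of r). At r = 0.5, 0.7 and 0.9:

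- The variance ratios were 0.752, 0.855 and 0.962.
- The slope of the change contrast on the baseline difference was −0.51, −0.30 and −0.10, against about zero for ANCOVA.
- Both estimators averaged to zero under no effect, so neither is biased over randomizations.
- ANCOVA on the change and ANCOVA on the follow-up score gave the same treatment difference to rounding error.

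**The case against.** The strongest reply is that X.B nowhere calls the changes raw or unadjusted. It names the composite itself as the outcome variable and leaves the model open. Changes can be analyzed with the Visit 2 score as covariate, and then nothing is lost. This stands in part. A reader might infer that the plan prescribes an unadjusted comparison, and the text does not go that far. It does describe a comparison of changes with no covariate, next to an analysis where the covariate is spelled out, so the unadjusted version is the natural reading and nothing rules it out.

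Other stronger readings are tempting and are not supported:

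- **That outcome 1 is the only analysis using the full battery at weeks 3 and 6.** The primary objective composite already includes the MCG, SDMT and Stroop tests, which are given on treatment only at those weeks, and it is baseline-adjusted.
- **That outcome 3 is unadjusted.** Its cognitive and behavioral scores closely parallel the objective and subjective composites, for which X.B does specify ANCOVA. Only an explicit link is missing.
- **That the retained imbalance rivals the effect the trial looks for.** X.A spaces four arms equally over 0.24, which is 0.24/3 = 0.08 between neighbors, but only at maximum effect. It assumes equal arms at week 6. Without the composite SD, the imbalance cannot be put on the z scale at all.

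It can also be objected that r may be high. Under one possible reading of X.A (a group by time test with compound symmetry), 80% power at 18 per group needs a correlation of about 0.92 if the SD is 0.5, or 0.98 if it is 1. The ratio would then be 0.96 or 0.99, and the 1.4% slope cost would take up a good part or all of the gain. The plan states neither that test nor those values, so this widens the range downward without settling it.

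**Conclusion.** The point holds as a minor one. Secondary outcome 1 is written as a comparison of changes without a baseline covariate, and secondary outcome 4 is silent on baseline, while the primary composites are adjusted for the Visit 2 score. If the text is followed in its natural sense, ANCOVA would cut the variance by 25% at r = 0.5, 15% at 0.7, 10% at 0.8 and 5% at 0.9, before the 1.4% slope cost. That is equivalent to about 6, 3, 2 or 1 further subjects per arm.

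These figures rest on assumed values of r, equal variances at the two visits and 19 completers per arm. The gain becomes negligible as r approaches 1.

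A reader might infer bias. There is none over randomizations; the imbalance matters only conditionally, given the baseline difference actually observed. The primary inference is not touched.

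**What to change.** Add one sentence to X.B: secondary outcomes 1 and 4, and outcome 3 for consistency, are analyzed with the Visit 2 score of the same measure as a covariate, together with the other covariates used in the primary analysis. For outcome 1 the dependent variable may be either the change to weeks 3 and 6 or the score at those weeks. With the covariate in the model, both give the same treatment difference, so the word change can stay.

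The cost is wording only. VI.E places Visit 2 testing before the first dose, and Appendix A schedules the full battery at that visit, so no new data are needed. The statistical price is the 1.4% for estimating the slope. The sentence also removes the option of choosing between adjusted and unadjusted results after the data are seen.
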